6.5.1 Dose Delay and Toxicity-related Discontinuation Guidelines

If criteria for tamibarotene/placebo dose hold are met (Table 1), azacitidine dosing may continue, unless criteria for azacitidine hold are also met.

If criteria for azacitidine dose hold are met (Table 1), tamibarotene/placebo dosing may continue, unless criteria for tamibarotene/placebo hold are also met. Day 1 of the next treatment cycle is delayed until azacitidine dosing may resume.

If implementation of dose modification guidelines described in Table 1 (including dose holds and reductions) was not sufficient to adequately manage toxicity, the relevant study drug(s) should be discontinued. Discontinuation of only tamibarotene/placebo or only azacitidine while continuing administration of the other study drug may occur. If only azacitidine is permanently discontinued, Day 1 of the next treatment cycle may resume within 3 days of the decision to discontinue azacitidine.

If implementation of dose modifications described in Table 1 are insufficient to adequately manage toxicity and discontinuation of both tamibarotene/placebo and azacitidine is required, the patient should have an EoT Visit.

6.5.2 Phototoxicity

Tamibarotene did not demonstrate phototoxic potential in Neutral Red Uptake Phototoxicity Assay (see IB). Furthermore, phototoxicity has not been reported in clinical studies of tamibarotene to date.

6.5.3 Hypertriglyceridemia

Significant increases in both cholesterol and triglycerides have been reported with tamibarotene in patients with APL. Similarly, increases in triglycerides have been reported in patients with AML. Based upon these findings, tamibarotene should be cautiously administered to patients with a disposition of hypertriglyceridemia such as those with diabetes mellitus, obesity, alcoholism, or abnormal lipid metabolism.

6.6 Continued Access to Study Drug After the End of the Study

At the time of study termination, if there are patients benefitting from treatment in the opinion of the investigator, the investigator should contact the medical monitor to discuss the possibility of treatment continuation.

6.8 Concomitant Therapy

Concomitant therapy must be documented as described in Section 8.2.1.

6.8.1 Cytotoxic or Investigational Therapy

No concomitant cytotoxic or investigational therapy is allowed during the study.

6.8.2 Growth Factors

Growth factor treatment must be discontinued at least 2 weeks prior to starting study drug. Short-term use of myeloid growth factor is allowable for treatment of life-threatening infections.

6.8.3 Thrombopoietin Receptor Agonists

Thrombopoietin receptor agonists must be discontinued prior to starting study drug and are not allowed during the study.

6.8.4 Oral Hydroxyurea

[figure not shown]
Hydroxyurea treatment must be discontinued prior to starting study drug and is not allowed during the study.

6.8.5 Platelet Transfusions

Administration of platelet transfusions may be utilized throughout the study, as clinically determined.

6.8.6 Red Blood Cell Transfusions

Administration of RBC transfusions may be utilized throughout the study, as clinically determined.

6.8.8 Antifibrinolytic

Investigators should be advised of the potential for thrombosis observed when drugs similar to tamibarotene (e.g., ATRA/tretinoin) have been combined with an antifibrinolytic. Antifibrinolytic medicines should be used with caution while on study drug.

6.8.9 Retinoic Acid Syndrome

Patients should be carefully monitored for the development of retinoic acid syndrome (RAS). High-dose dexamethasone (i.e., 10 mg/m^2 intravenous twice daily), and supportive measures (e.g., diuretics, dialysis, mechanical ventilation) as needed, should be implemented at the earliest suspicion of RAS. Glucocorticoid therapy should continue until complete disappearance of symptoms and then tapered. Tamibarotene/placebo therapy should be temporarily discontinued until RAS is considered controlled and <Grade 2.

6.8.10 Multivitamin and Supplements

Vitamin A supplements (>10,000 IU/day) are not allowed while on study drug.

6.8.11 Antacids and Proton Pump Inhibitors

Antacids, H₂-receptor antagonists such as cimetidine, and proton pump inhibitors such as omeprazole should be used with caution while on study drug, as exposure to tamibarotene may be increased when these products are used concomitantly. Patients must be monitored for AEs, with dose adjustments for toxicity as described in Section 6.5.

7 DISCONTINUATION OF STUDY DRUG AND PATIENT DISCONTINUATION/WITHDRAWAL

7.1 Discontinuation of Study Drug Administration

Patients will continue to receive study drug until they meet one of the following criteria:

- An unacceptable toxicity, including AEs that would result in permanent discontinuation of study drug (Section 6.5)
- An AE related to study drug that requires ≥28 days (1 cycle) of dose interruption of both tamibarotene/placebo and azacitidine
- Failure to achieve a minimum response of HI in at least 1 cell lineage following the completion of the Cycle 7 Day 1 response assessment
- Disease progression/relapse
- Pregnancy
- Decision to pursue post-remission therapy (such as HSCT) or an alternative anticancer therapy; consolidation treatment with HSCT following the receipt of study drug is permissible.
- Patient withdraws consent for further study drug (interventional therapy) administration. The site should clarify with the patient if they maintain consent to follow up visits and calls after the end of study drug administration.
- Investigator determines it is in the best interest of the patient to discontinue study drug (interventional therapy) administration.

An EoT Visit should occur within 3 days of the last dose of study drug (or within 3 days of decision to permanently stop study drug treatment, if this decision directly follows a period when study drug has been on hold) and before the start of any subsequent anticancer therapy. A Safety Follow-up Visit should occur 30 days (\pm 3 days) after the EoT Visit and if possible before the start of any subsequent anticancer therapy. If the EoT Visit occurs \geq 30 days after the last dose of study drug, it may be combined with the Safety Follow-up Visit.

Patients will continue participation in all applicable follow-up assessments according to the SoA (Section 1.3).

7.2 Discontinuation of Study Participation by Patient's Withdrawal of Informed Consent

• If a patient withdraws consent to study participation, study drug administration will be terminated and no additional follow up will occur. Public sources may be searched for vital status information.

- The sponsor may retain and use any data collected before withdrawal of consent for study participation.
- If a patient withdraws their informed consent, he/she may request destruction of any samples taken and not yet tested, and the investigator must document this in the patient's medical records.

7.3 Lost to Follow-up

A patient will be considered lost to follow-up if he or she repeatedly fails to comply with the protocol and is unable to be contacted by the study site.

The following actions must be taken if a patient fails to return to the clinic for a required study visit:

- The site must attempt to contact the patient and reschedule the missed visit as soon as possible, counsel the patient on the importance of maintaining the assigned visit schedule, and ascertain whether or not the patient wishes to and/or should continue in the study.
- Before a patient is deemed lost to follow up, the investigator or designee must make every effort to regain contact with the patient (where possible, 3 telephone calls and, if necessary, a certified letter to the patient's last known mailing address or local equivalent methods). These contact attempts should be documented in the patient's medical record.
- Should the patient continue to be unreachable, he/she will be considered to have discontinued from the study.
- Site personnel, or an independent third party, will attempt to collect the vital status of the patient within legal and ethical boundaries for all patients randomized. Public sources may be searched for vital status information. If vital status is determined as deceased, this will be documented, and the patient will not be considered lost to follow-up. Sponsor personnel will not be involved in any attempts to collect vital status information.

Discontinuation of specific sites or of the study as a whole are handled as part of Appendix 1.

8 STUDY ASSESSMENTS AND PROCEDURES

- Study procedures and their timing are summarized in the SoA (Section 1.3). Protocol waivers or exemptions are not allowed.
- Adherence to the study design requirements, including those specified in the SoA (Section 1.3), is essential and required for study conduct.
- All pre-screening and screening evaluations must be completed and results reviewed prior to dosing on Cycle 1 Day 1. Minimal details of all patients screened will be captured to confirm eligibility or record reasons for screening failure, as applicable.

- Procedures conducted as part of the patient's routine clinical management (e.g., blood count) and obtained before signing of the informed consent form (ICF) may be utilized for screening purposes, provided the procedures met the protocol-specified criteria and were performed within the time frame defined in the SoA (Section 1.3). Screening hematology parameter evaluation must be performed at least 7 days following any blood product transfusion.
- The maximum amount of blood collected from each patient over the duration of the study is specified in the ICF.
- Repeat or unscheduled samples may be taken for safety reasons or for technical issues with the samples.
- For all randomized patients, any untoward medical occurrences that happen before the first dose of the study drug should be captured as a part of medical history.

8.1 Efficacy Assessments

Planned time points for all efficacy assessments are provided in the SoA (Section 1.3). Unscheduled efficacy assessments during the study will also be collected in the electronic data capture (EDC) system.

8.1.1 Response Assessment

Responses are evaluated per the modified IWG MDS criteria (Cheson 2006). A copy of the criteria is provided in Appendix 8. Note that resolution of dysplasia is not required for achievement of an IWG response. Physical examinations (Section 8.2.3) are scheduled at the time of all response assessments and include an assessment for the presence of extramedullary AML. Additional unscheduled hematology evaluations may be performed up to 2 weeks after the bone marrow aspiration, for those patients in marrow CR without full peripheral blood count recovery at the time of the bone marrow aspirate, to assess whether they meet IWG criteria for CR based on the results of this additional hematology evaluation. The CR date is assigned as the date of marrow sampling or peripheral count recovery, whichever is later.

In addition to on-treatment assessments, patients who have not progressed/relapsed will enter the Disease Follow-up period, during which response assessments will be performed every 3 months for response assessment until disease progression/relapse, death, or the occurrence of the expected number of OS events to support the final OS analysis, whichever occurs first. Response assessments during Disease Follow-up visits where the bone marrow aspirates are not performed, are based on hematology evaluation and physical examination findings.

Patients who progress/relapse will enter Survival Follow-up and will be followed to document the start of subsequent anticancer therapy, the date of disease progression/relapse, the date of transformation to AML, and OS status until the expected number of OS events to support the final OS analysis is observed.

8.1.2 Bone Marrow Sample Collection

A screening bone marrow aspirate will be performed, with samples for local assessment of blast count, cytogenetics, MDS-associated gene mutations, and immunophenotype. A bone marrow biopsy may be performed at investigator's discretion to supplement the interpretation of the bone marrow aspirate. In addition, it is mandatory that an aspirate smear will be sent to the Central Laboratory for central morphologic review. An additional aspirate sample should be collected if possible and sent to the Central Laboratory for exploratory analyses.

Bone marrow aspirate smears collected within 30 days of Cycle 1 Day 1 as a part of standard of care (pre-consent) are acceptable to support both local assessments and central review.

Response assessment bone marrow aspirates will be collected on Day 1 of Cycles 2 and 4, followed by every third cycle (7, 10, 13, etc.), and at EoT, with bone marrow aspirates collected at other times as clinically determined. Following the Cycle 7 Day 1 response assessment, those in CR may have the frequency of bone marrow aspirates for response assessment reduced to every 6 cycles. The samples for the local assessment of response (blast count and cytogenetics) are required. In addition, an aspirate smear will be collected and sent to the Central Laboratory for central review. At Cycle 4 Day 1, Cycle 7 Day 1, every 6 cycles thereafter, as well as at EoT, an additional aspirate sample will be collected and sent to the Central Laboratory for exploratory analyses (Section 8.6.3). A bone marrow biopsy may be performed at investigator's discretion to supplement the interpretation of the bone marrow aspirate.

During the Disease Follow-up period, the response assessment bone marrow aspirates will be collected every 3 months during the Disease Follow-up period, with bone marrow aspirates collected at other times as clinically determined. Patients in CR may have the frequency of bone marrow aspirates for response assessment reduced to every 6 months. The samples for the local assessment of response (blast count and cytogenetics) are required. In addition, an aspirate smear for central review will be collected and sent to the Central Laboratory. An additional aspirate sample should be collected if possible and sent to the Central Laboratory for exploratory analyses (Section 8.6.3). A bone marrow biopsy may be performed at investigator's discretion to supplement the interpretation of the bone marrow aspirate.

Instructions for the collection and handling of the bone marrow samples will be provided separately in the Laboratory Manual.

8.1.3 Hematologic Improvement

Baseline hemoglobin and platelet values will be collected at the Screening Visit. The screening hematology parameter evaluation must be performed prior to or at least 7 days following any blood product transfusion (see Appendix 8).

8.1.4 Transformation to AML

A diagnosis of AML (per WHO; Vardiman 2009, Arber 2016) is defined by either:

• ≥20% blasts in the peripheral blood or bone marrow

OR

• development of myeloid sarcoma

8.1.5 Blood Product Transfusions

All RBC and platelet transfusions received by the patient from 16 weeks prior to randomization through the Disease Follow-up period will be recorded.

8.1.6 Overall Survival

All patients will be followed for OS every 3 months until the expected number of OS events to support the final OS analysis is observed. If the patient withdraws consent for study participation (Section 7.2) or is lost to follow-up (Section 7.3), public sources may be searched for vital status information.

8.2 Safety Assessments

Planned time points for all safety assessments are provided in the SoA (Section 1.3).

8.2.1 Prior, Concomitant, and Subsequent Medication Review

Every medication (including over-the-counter or prescription medicines, recreational drugs, vitamins, and/or herbal supplements), vaccines, and blood products used by the patient within 30 days of Cycle 1 Day 1 or at any time during the course of the study treatment, up to the Safety Follow-up Visit, must be documented, including:

- reason for use;
- dates of administration, including start and end dates;
- dosage information, including dose and frequency.

The medical monitor should be contacted if there are any questions regarding concomitant or prior therapy.

Subsequent anticancer therapies (including HSCT) following EoT will be recorded.

8.2.2 ECOG Performance Status

A copy of the ECOG Performance Status criteria is provided in Appendix 5.

8.2.3 Physical Examinations

 A complete physical examination will include, at a minimum, assessments of the Cardiovascular, Respiratory, Gastrointestinal, and Neurological systems and an assessment for the presence of extramedullary AML. The skin examination should include monitoring for cancerous and pre-cancerous lesions and appropriate referral to dermatologic evaluation and care, as clinically indicated.

- An abbreviated physical examination will include, at a minimum, assessments of the skin, lungs, Cardiovascular system, and abdomen (liver and spleen) and an assessment for the presence of extramedullary AML. The skin examination should include monitoring for cancerous and pre-cancerous lesions and appropriate referral to dermatologic evaluation and care, as clinically indicated.
- Investigators should pay special attention to clinical signs related to previous serious illnesses.

8.2.4 Vital Signs

- Body temperature, pulse rate, respiratory rate, and blood pressure will be assessed.
- Blood pressure and pulse measurements should be assessed with a completely automated device. Manual techniques will be used only if an automated device is not available.
- Blood pressure and pulse measurements should be preceded by at least 5 minutes of rest for the patient in a quiet setting without distractions (e.g., television, cell phones).
- Vital signs should be measured in a semi-supine position after 5 minutes rest and will include temperature, systolic and diastolic blood pressure, pulse rate, and respiratory rate.

8.2.5 Electrocardiograms

Triplicate 12-lead ECGs will be obtained using an ECG machine that automatically calculates the heart rate and measures PR, QRS, QT, and QTc intervals. Fridericia formula should be used to calculate QTc. Three individual ECG tracings should be obtained as closely as possible in succession, but no more than 2 minutes apart.

ECGs should be performed after an approximately 10-minute rest period.

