1.3 Schedule of Activities

	Pre- screening (a) Day -45 to C1D1	Screening (a) Day -30 to C1D1		•				End of Treatment (EoT) (c)	Safety Follow- up (d) 30d post EoT (±3d)	Disease Follow- up (e) q3mo post EoT (±14d)	Survival Follow- up (f) q3mo post EoT (±14d)		
Study Day			D1 (g)	D2-7 (±2d)	D8 (±1d)	D22 (±1d)	D1 (±3d)	D2-7 (±2d)	D15 (±2d) (h)				
Pre-screening Informed Consent	X												
Main Informed Consent		X											
Eligibility Review (i)		X	X (i)										
Eligibility Approval Form (i)		X	X (i)										
Randomization (j)			X										
Medical History (k)		X	X										
Demographics		X											
ECOG Status		X	X				X			X	X		
Height		X											
Weight		X	X		X	X	X			X	X		
Vital Signs (l)		X	X	X (1)	X	X	X	X (1)	X	X	X		
Physical Examination (m) (n)		X	X		X (n)	X (n)	X (n)			X	X	X (n)	
Hematology (o), (p), (q)		X (p)	X		X	X	X (q)			X	X	X	

	Pre- screening (a) Day -45 to C1D1	Screening (a) Day -30 to C1D1			cle 1 Days		Cycles 2+ 28 Days Each (b)			End of Treatment (EoT) (c)	Safety Follow- up (d) 30d post EoT (±3d)	Disease Follow- up (e) q3mo post EoT (±14d)	Survival Follow- up (f) q3mo post EoT (±14d)
Study Day			D1 (g)	D2-7 (±2d)	D8 (±1d)	D22 (±1d)	D1 (±3d)	D2-7 (±2d)	D15 (±2d) (h)				
Serum Chemistries (o)		X	X		X	X	X			X	X		
Coagulation (o)		X	X				X			X	X		
Triglycerides, Total Cholesterol (o)		X	X				X			X	X		
Hepatitis Panel (r)		X											
Urinalysis (o)		X	X				X			X	X		
Pregnancy Test (s)		X	X				X			X	X		
Triplicate ECG (t)		X			X	X			X				
AE Monitoring (u)			X	X	X	X	X	X	X	X	X		
Prior/Concomitant Medication Review (v)		X	X	X	X	X	X	X	X	X	X		
RBC and Platelet Transfusions Recorded (w)		X	X	X	X	X	X	X	X	X	X	X	
Dosing Compliance/Diary Review					X	X	X		X	X			
HRQOL (EORTC QLQ-C30, EQ-5D-5L)		X	X				X			X	X	X	
Subsequent Anticancer Therapies (x)											X	X	X

CONFIDENTIAL

	Prescreening (a) Day -45 to C1D1	Screening (a) Day -30 to C1D1							End of Treatment (EoT) (c)	Safety Follow- up (d) 30d post EoT (±3d)	Disease Follow- up (e) q3mo post EoT (±14d)	Survival Follow- up (f) q3mo post EoT (±14d)	
Study Day			D1 (g)	D2-7 (±2d)	D8 (±1d)	D22 (±1d)	D1 (±3d)	D2-7 (±2d)	D15 (±2d) (h)				
Response Assessment (q), (y)							X (q), (y)			X (y)		X (y)	
Bone Marrow Aspirate		X (z)					X (aa)			X (aa)		X (bb)	
Transformation into AML							X			X		X	X
Overall Survival													X
Tamibarotene or Placebo (cc)					Dosii	ng D8-2	28 of ea	ich Cyc	le (cc)				
Azacitidine (dd)			X	X (dd)			X	X (dd)					

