- (e) Patients who have not progressed/relapsed will enter the Disease Follow-up period. Visits should occur every 3 months for response assessment until disease progression/relapse, death, or the occurrence of the expected number of OS events to support the final OS analysis, whichever occurs first. Disease Follow-up Visit window is ±14 days.
- (f) Patients who progress/relapse will be followed to document the start of subsequent anticancer therapy, the date of disease progression/relapse, the date of transformation to AML, and OS status by telephone (or another appropriate method) until the expected number of OS events to support the final OS analysis is observed. Survival Follow-up Visit contact window is ±14 days.
- (g) C1D1 assessments must be performed prior to study drug administration.
- (h) Cycles 2 through 4 only.
- (i) Eligibility review and approval by Sponsor or designee (via Eligibility Approval Form) must be completed prior to randomization.
- (j) Patients can be randomized earlier than C1D1, but within 72 hours of the first dose of study drug, to accommodate operational needs.
- (k) For all randomized patients, any untoward medical occurrences that happen before the first dose of the study drug should be captured as a part of medical history.
- (l) If administration of the 6th and 7th doses of azacitidine of the cycle is delayed to Days 8 and 9 (see footnote (dd)), the vital sign evaluation will shift from Days 6 and 7 to Days 8 and 9 to parallel azacitidine administration. C1D8 vital sign evaluation is required for all patients.
- (m) Definitions for the "full" and "abbreviated" physical examination are provided in Section 8.2.3; both must include an assessment for the presence of extramedullary AML.
- (n) Abbreviated physical examination will be performed at C1D8, C1D22, D1 of Cycles 2+, and at each Disease Follow-up Visit (see Section 8.2.3).
- (o) Laboratory assessments will be performed locally.
- (p) Screening hematology parameter evaluation must be performed prior to or at least 7 days following any blood product transfusion.
- (q) Additional unscheduled hematology evaluations may be performed up to 2 weeks after the bone marrow aspiration, for those patients in marrow CR without full peripheral blood count recovery at the time of the bone marrow aspirate, to assess whether they meet IWG criteria for CR.
- (r) See Section 10.2 for details.

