- (s) A pregnancy test (high-sensitivity urine or serum) must be performed for women of childbearing potential.
- (t) ECGs should be performed after an approximately 10-minute rest period.
- (u) AEs and SAEs will be captured from the time of the first study drug administration through the Safety Follow-up Visit.
- (v) Every medication within 30 days of C1D1 or at any time during the course of the study treatment, up to the **Safety Follow-up Visit**, must be documented.
- (w) All RBC and platelet transfusions received by the patient from 16 weeks prior to randomization through the Disease Follow-up period will be recorded. Per the IWG 2006 response criteria, RBC transfusions entered into the corresponding eCRF in EDC should include only those administered for a hemoglobin level of ≤9 g/dL.
- (x) Subsequent anticancer therapies (including allogeneic HSCT) following EoT will be recorded.

- (y) Response assessments will be performed on D1 of Cycles 2 and 4, followed by every third cycle (7, 10, 13, etc.), at the EoT Visit and at each Disease Follow-up Visit, with additional assessments performed if clinically determined. Following the C7D1 response assessment, those in CR may have the frequency of bone marrow aspirates for response assessment reduced to every 6 cycles, with intervening response assessments based on hematology evaluation and physical examination findings.
- (z) A screening bone marrow aspirate will be performed, with samples for local assessment of **blast count**, **cytogenetics**, **MDS-associated gene mutations**, and **immunophenotype**. A bone marrow biopsy may be performed at investigator's discretion to supplement the interpretation of the bone marrow aspirate. In addition, it is mandatory that an aspirate smear will be sent to the **Central Laboratory** for **central morphologic review**. An additional aspirate sample should be collected if possible and sent to the **Central Laboratory** for **exploratory analyses**. Bone marrow aspirate smears collected within 30 days of Cycle 1 Day 1 as a part of standard of care (pre-consent) are acceptable to support both local assessments and central review.

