- (aa) Response assessment bone marrow aspirates will be collected on Day 1 of Cycles 2 and 4, followed by every third cycle (7, 10, 13, etc.), and at EoT, with bone marrow aspirates collected at other times as clinically determined. Following the C7D1 response assessment, those in CR may have the frequency of bone marrow aspirates for response assessment reduced to every 6 cycles. The samples for the local assessment of response (blast count and cytogenetics) are required. In addition, an aspirate smear will be collected and sent to the Central Laboratory for central review. At C4D1, C7D1, every 6 cycles thereafter, as well as at EoT, an additional aspirate sample will be collected and sent to the Central Laboratory for exploratory analyses (Section 8.6.3). A bone marrow biopsy may be performed at investigator's discretion to supplement the interpretation of the bone marrow aspirate.
- (bb) Response assessment bone marrow aspirates will be collected every 3 months during the Disease Follow-up period, with bone marrow aspirates collected at other times as clinically determined. Patients in CR may have the frequency of bone marrow aspirates for response assessment reduced to every 6 months. The samples for the local assessment of response (**blast count** and **cytogenetics**) are required. In addition, an aspirate smear for **central review** will be collected and sent to the Central Laboratory. An additional aspirate sample should be collected if possible and sent to the Central Laboratory for exploratory analyses (Section 8.6.3). A bone marrow biopsy may be performed at investigator's discretion to supplement the interpretation of the bone marrow aspirate.
- (cc) The morning dose of tamibarotene/placebo will be taken in the clinic on C1D8, C1D22, and D15 of Cycles 2 through 4; date/time of dose should be recorded.
- (dd) If dosing on Days 6 and 7 of a cycle is not possible due to logistical limitations, these doses may be delayed to Days 8 and 9. Tamibarotene/placebo is permitted to overlap with azacitidine on Days 8 through 9 of this alternative schedule. If criteria for azacitidine dose hold are met (Table 1), tamibarotene/placebo dosing may continue, unless criteria for tamibarotene/placebo hold are also met. D1 of the next treatment cycle is delayed until azacitidine dosing may resume.
- (ee) Peripheral blood samples will be sent to the Almac Diagnostics Laboratory for assessment of RARA biomarker to determine study eligibility.

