- (ff) For evaluation of MDS molecular features associated with response to drug treatment and loss of response to drug treatment (Section 8.6.3).
- (gg) The morning dose of tamibarotene/placebo will be taken in the clinic on C1D8 and C1D22; date/time of dose should be recorded. The date/time of the C1D21 evening dose of tamibarotene/placebo should also be recorded. Three PK blood samples should be obtained on C1D8 and on C1D22, and collection time/date recorded: 1) pre-dose; 2) 1 hour post-dose (±30 min); 3) 3 hours post-dose (±30 min).

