7.6 Safety Evaluation

All safety analyses will be conducted for Safety Analysis Set 1, unless otherwise specified. For safety analysis presented by study visit, the baseline value will be defined as the last non-missing value reported prior to the first study drug administration.

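### The protocol does not say whether on-treatment ECGs come before or after the same-day tamibarotene/placebo dose, so the by-visit QTcF tables can mix unexposed, trough and post-dose readings

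*Protocol*

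**What the plan says.** Protocol 1.3 (Schedule of Activities) places triplicate ECGs at Screening, Cycle 1 Day 8 (C1D8), Cycle 1 Day 22 (C1D22) and Day 15 (D15) of later cycles. A footnote limits the D15 visit to Cycles 2 to 4.

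Protocol 8.2.5 sets two conditions on how the ECG is taken: "ECGs should be performed after an approximately 10-minute rest period" and "Three individual ECG tracings should be obtained as closely as possible in succession, but no more than 2 minutes apart". Footnote (t) of the schedule repeats only the rest period. SAP 6.4.2.3.2 describes the machine and the Fridericia correction and adds no timing.

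Dosing on these days is specified more closely. Footnote (cc) says: "The morning dose of tamibarotene/placebo will be taken in the clinic on C1D8, C1D22, and D15 of Cycles 2 through 4", with the date and time of the dose recorded. Footnote (gg) says: "Three PK blood samples should be obtained on C1D8 and on C1D22, and collection time/date recorded", and fixes the draws at pre-dose, 1 hour and 3 hours post-dose, each post-dose draw within 30 minutes either way.

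For safety summaries by visit, SAP 7.6 says that "the baseline value will be defined as the last non-missing value reported prior to the first study drug administration". Protocol section 6 defines study drug to include every trial intervention from Cycle 1 Day 1, so azacitidine counts. Protocol 9.4.4 and SAP 7.6.3.2 tabulate prolonged QTcF by visit and also categorise change from baseline. Neither distinguishes pre-dose from post-dose readings.

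**The concern.** ECG results belong to the safety endpoint in Protocol section 3. The sponsor treats QTc as relevant: it is an exclusion criterion and has its own outlier and change tables. Those tables should compare patients exposed to tamibarotene with patients who are not.

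The text does not secure that contrast. C1D8 is the first tamibarotene day. An ECG taken that morning before the dose compares two arms that have both had only azacitidine, yet it enters the tables as a post-baseline, on-treatment reading. At the other four visits an ECG before the morning dose is a trough reading. A table that mixes these with post-dose readings, with nothing to separate them, could look reassuring about repolarisation for a reason unrelated to the drug.

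**Working it through.** The plan gives no figure to reproduce here, so the check sets the passages side by side and counts visits.

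**Step 1: count the visits.** C1D8 and C1D22 give 2; D15 of Cycles 2, 3 and 4 gives 3. Total: 2 + 3 = 5 scheduled on-treatment ECG visits (Protocol 1.3).

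**Step 2: compare with dosing.** Footnote (cc) names the same days, so 5 of 5 ECG visits have a timed in-clinic dose. Visits with a stated ECG time relative to that dose: 0 of 5.

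**Step 3: what the text permits if the ECG comes first.**

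| Visit | Tamibarotene exposure at a pre-dose ECG | PK draws that day |
|---|---|---|
| C1D8 | none (dosing starts on Day 8) | pre-dose, 1 h, 3 h |
| C1D22 | trough | pre-dose, 1 h, 3 h |
| D15, Cycles 2 to 4 | trough | none |

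**Step 4: how a pre-dose C1D8 ECG is classified.** First study drug is azacitidine on Cycle 1 Day 1. Baseline is the last value before that. A C1D8 ECG is therefore post-baseline whether or not tamibarotene has been taken.

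**Step 5: whether the SAP can separate the readings later.** SAP 7.1.2 groups data by nominal visit label and averages continuous values recorded on the same day. A pre-dose and a post-dose QTcF from one day would thus be blended. Without a recorded ECG time, a single reading cannot be placed on either side of the dose.

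**Step 6: dilution at C1D8.** Let f be the share of C1D8 ECGs in the tamibarotene arm taken before the first dose; f is unknown. Let E be the mean QTcF effect at the post-dose ECG time. The mean effect shown is f × 0 + (1 − f) × E = (1 − f) × E.

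- f = 0: 100% of E
- f = 0.5: 50% of E
- f = 1: 0% of E

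The loss at the other four visits depends on how far concentration and any QT effect fall by trough. The documents give no half-life, peak time or QT effect size, so it is left uncomputed.

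**The case against.** The case on the other side has several parts.

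- **The ECGs are linked to dosing by day.** This is correct. D15 of Cycles 2 to 4 has an in-clinic dose but no PK draw, which suggests that the dose may have been placed there for the ECG. That is inference, and the order within the day is still unwritten.
- **A reader might infer that sites will take every ECG before the dose, so that C1D8 shows no difference by construction.** No passage describes such a site routine. The text permits it, but f could be zero.
- **A reader might assume a peak time and half-life and quote the percentage of the effect lost at trough.** Nothing in the documents supports any particular values, so such percentages say nothing about this trial.
- **A reader might infer that QTcF cannot be related to concentration.** That goes too far. Dose times are recorded, PK is sampled on C1D8 and C1D22, and Protocol 6.3 plans a population PK model. If ECG clock times are held, concentration at the ECG could be predicted. The eCRF may capture them, but the protocol and SAP do not require it.
- **No QT effect of tamibarotene is reported in these documents, and other safeguards exist.** Clinically significant ECG findings are reportable as adverse events, and investigator-graded ECGs are summarised as shifts to the worst post-baseline category. This stands and limits the seriousness. These safeguards still use ECGs taken at the same unspecified times.
- **Counting C1D8 as post-baseline follows the SAP definition.** It does, and it is not an error. Dropping pre-dose C1D8 ECGs would discard azacitidine-exposed safety data from both arms. Labelling them is enough.

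**Conclusion.** The point holds as a cheap improvement, not as an error or contradiction. All five scheduled on-treatment ECG visits have a timed in-clinic dose, and none has an ECG time relative to it. A site can comply fully and still produce one reading with no tamibarotene exposure and four at trough. The planned by-visit QTcF tables would not distinguish these from post-dose readings.

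The consequence is dilution of any tamibarotene effect on QTcF. At C1D8 the share of the effect that remains is 1 − f, anywhere from 0% to 100%; at the other visits it cannot be calculated. This rests on two unknowns: how often sites take the ECG before the dose, and whether tamibarotene affects QTcF at all. A reader might conclude that the trial will give false reassurance on cardiac safety. The documents show only that the plan does not rule this out. The primary and key secondary analyses are unaffected.

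**What to change.** In Protocol 8.2.5 and footnote (t) of the Schedule of Activities:

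- Require the triplicate ECG after the in-clinic dose. On C1D8 and C1D22, place it next to one of the existing post-dose PK draws. On D15 of Cycles 2 to 4, use a matching post-dose window. The sponsor should set the window from its PK data.
- Require the clock time of each ECG to be recorded.

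In SAP 7.6.3.2, state that a C1D8 ECG recorded before the first tamibarotene/placebo dose is kept, labelled pre-tamibarotene, and shown separately from the post-tamibarotene QTcF summaries. State also that SAP 7.1.2 same-day averaging does not combine readings from before and after the dose.

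The cost is one protocol sentence in two places, one recorded time per ECG, and two sentences in the SAP. No ECG is added. Patients already stay about 3 hours on C1D8 and C1D22 for PK, so the burden is a short wait at three D15 visits.
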